2.1.3 Efficacy endpoints

All efficacy measurements collected during the study will be considered for analyses, including those obtained after IMP discontinuation or introduction of rescue therapy (see [Section 2.5.4](#)).

HbA1c, 2-hour PPG, FPG, urine ACR, UGE, urine GCR, serum creatinine, and eGFR are measured/calculated in a central laboratory (see study flowchart in [\).](#) Body weight, SBP and DBP (see [Section 2.1.4.5](#)) are measured at on-site visits by the investigator. Patients requiring rescue are identified as those with the reason for treatment ticked “rescue therapy” in e-CRF “Medication” page.

Efficacy variables will be summarized in both standard international units and conventional units when applicable.

2.1.3.1 Primary efficacy endpoint(s)

Comparison of sotagliflozin 400 mg versus placebo in change from baseline to Week 26 in HbA1c (%).

2.1.3.2 Secondary efficacy endpoint(s)

The secondary efficacy endpoints are:

- Comparison of sotagliflozin 400 mg versus placebo for,
 - Change from Baseline to Week 26 in 2-hour PPG following a MM
 - Change from Baseline to Week 26 in FPG
 - Change from Baseline to Week 26 in body weight
 - Change from Baseline to Week 12 in SBP for patients with baseline SBP \geq 130 mmHg
 - Change from Baseline to Week 12 in SBP for all patients
 - Proportion of patients with HbA1c <6.5%, <7.0% at Week 26

Statistical Analysis Plan

Version: 3

Lexicon Pharmaceuticals Protocol No. EFC14833

Date of Issue: 21-Nov-2019

Covance Study ID: 000000150524

- Comparison of sotagliflozin 200 mg versus placebo for,
 - Change from Baseline to Week 26 in HbA1c
 - Change from Baseline to Week 26 in 2-hour PPG following a MM
 - Change from Baseline to Week 26 in body weight
 - Change from Baseline to Week 12 in SBP for all patients.

2.1.3.3 *Other efficacy endpoint(s)*

Comparison of sotagliflozin 400 mg and 200 mg doses versus placebo for,

- Change from Baseline to Week 12 in SBP for patients with baseline SBP <130 mmHg
- Changes from Baseline to Week 12 in diastolic blood pressure (DBP)
- Proportion of patients achieving SBP <130 mmHg for those with Baseline SBP \geq 130 mmHg
- Proportion of patients achieving DBP <80 mmHg for those with Baseline DBP \geq 80 mmHg
- Change from Baseline in:
 - Urine ACR, UGE, and urine GCR
 - Serum creatinine
 - eGFR
- Proportion of patients with reduction in body weight by \geq 2%, \geq 5%, and \geq 10% from Baseline
- Change from Baseline to Week 26 in SBP for all patients and for patients with Baseline SBP \geq 130 mmHg
- Proportion of patients requiring rescue for hyperglycemia

Comparison of sotagliflozin 200 mg versus placebo for,

- Change from baseline in FPG at Week 26
- Change from baseline in SBP at Week 12 for patients with Baseline SBP \geq 130 mmHg
- Proportion of patients with HbA1c <6.5%, <7.0% at Week 26

2.1.4 **Safety endpoints**

The safety analysis will be based on the reported adverse events, hypoglycemia, and other safety information, such as clinical laboratory data, vital signs, electrocardiogram (ECG), and physical examination, etc.

Statistical Analysis Plan

Version: 3

Lexicon Pharmaceuticals Protocol No. EFC14833

Date of Issue: 21-Nov-2019

Covance Study ID: 000000150524

Observation period

The observation period will be divided into 4 epochs:

- The **screening** epoch is defined as the time from the signed informed consent date up to the first administration of the double-blind IMP.
- The **treatment** epoch is defined as the time from the first administration of the double-blind IMP to the last administration of the double-blind IMP.
- The **residual treatment** epoch is defined as the time from the last administration of the double-blind IMP up to 10 days (1 day for hypoglycemia) after the last administration of the double-blind IMP.

The treatment-emergent adverse event (TEAE) period will include both **treatment** and **residual treatment** epochs.

- The **posttreatment** epoch is defined as the period of time starting the day after the end of the treatment-emergent adverse event period up to the last protocol-planned visit or the resolution/stabilization of all serious adverse events (SAE), adverse events of special interest (AESI) and events of special interest (EOSI), whichever is later.

The on-study observation period is defined as the time from start of double-blind treatment until the end of the study (defined as the last scheduled visit for those who completed the study and the date collected on e-CRF page “Completion of End of Study/Follow-up” for those who did not complete the study).

The post-study observation period is defined as the time from the day after the end of the study until the resolution/stabilization of all SAE, AESI and EOSI if applicable.

2.1.4.1 Hypoglycemia

Hypoglycemia will be identified as events recorded on the dedicated e-CRF “Hypoglycemic event information” page, and will be categorized as follows (see study protocol for further details):

Severe hypoglycemia

Severe hypoglycemia is an event requiring assistance of another person to actively administer carbohydrate, glucagon, intravenous glucose or other resuscitative actions. These episodes may be associated with sufficient neuroglycopenia to induce seizure, unconsciousness or coma.

Self-monitored plasma glucose values may not be available, but neurological recovery attributable to the restoration of plasma glucose to normal is considered sufficient evidence that the event was induced by a low plasma glucose concentration.

Severe hypoglycemia is identified in e-CRF “Hypoglycemic event information” page as those documented as,

1. To the question “Countermeasure Administration”, ticked the option “Subject was Not Capable of Treating Self and Required Assistance”, and

Statistical Analysis Plan

Version: 3

Lexicon Pharmaceuticals Protocol No. EFC14833

Date of Issue: 21-Nov-2019

Covance Study ID: 000000150524

2. To the question “Were Symptoms Present”, ticked “Yes”.

Documented symptomatic hypoglycemia

Documented symptomatic hypoglycemia is an event during which typical symptoms of hypoglycemia accompanied by a measured plasma glucose concentration of ≤ 3.9 mmol/L (≤ 70 mg/dL).

Clinical symptoms that are considered to result from a hypoglycemic episode are eg, increased sweating, nervousness, asthenia/weakness, tremor, dizziness, increased appetite, palpitations, headache, sleep disorder, confusion, seizures, unconsciousness, or coma.

Documented symptomatic hypoglycemia is identified in e-CRF “Hypoglycemic event information” page as those documented as,

1. To the question “Countermeasure Administration”, NOT ticked the option “Subject was Not Capable of Treating Self and Required Assistance”, and
2. To the question “Were Symptoms Present”, ticked “Yes”, and
3. With a plasma glucose value before countermeasure ≤ 3.9 mmol/L (≤ 70 mg/dL).

Asymptomatic hypoglycemia

Asymptomatic hypoglycemia is an event not accompanied by typical symptoms of hypoglycemia but with a measured plasma glucose concentration ≤ 3.9 mmol/L (≤ 70 mg/dL).

Asymptomatic hypoglycemia is identified in e-CRF “Hypoglycemic event information” page as those documented as,

1. To the question “Countermeasure Administration”, NOT ticked the option “Subject was Not Capable of Treating Self and Required Assistance”, and
2. To the question “Were Symptoms Present”, ticked “No”, and
3. With a plasma glucose value before countermeasure ≤ 3.9 mmol/L (≤ 70 mg/dL).

Probable symptomatic hypoglycemia

Probable symptomatic hypoglycemia is an event during which symptoms of hypoglycemia are not accompanied by a plasma glucose determination, (but that was presumably caused by a plasma glucose concentration ≤ 3.9 mmol/L [≤ 70 mg/dL]), ie, symptoms treated with oral carbohydrate without a test of plasma glucose.

Probable symptomatic hypoglycemia is identified in e-CRF “Hypoglycemic event information” page as those documented as,

1. To the question “Countermeasure Administration”, NOT ticked the option “Subject was Not Capable of Treating Self and Required Assistance”, and
2. To the question “Were Symptoms Present”, ticked “Yes”, and
3. With no plasma glucose value before countermeasure, and

Statistical Analysis Plan

Version: 3

Lexicon Pharmaceuticals Protocol No. EFC14833

Date of Issue: 21-Nov-2019

Covance Study ID: 000000150524

4. To the question “Did this countermeasure lead a significant improvement or prompt recovery?”, ticked “Yes”.

Relative hypoglycemia

Relative hypoglycemia, recently termed “pseudo-hypoglycemia” is an event during which the patient reports typical symptoms of hypoglycemia, and interprets the symptoms as indicative of hypoglycemia, but with a measured plasma glucose concentration >3.9 mmol/L (>70 mg/dL).

Relative hypoglycemia is identified in e-CRF “Hypoglycemic event information” page as those documented as,

1. To the question “Countermeasure Administration”, NOT ticked the option “Subject was Not Capable of Treating Self and Required Assistance”
2. To the question “Were Symptoms Present”, ticked “Yes”, and
3. With a plasma glucose value before countermeasure >3.9 mmol/L (>70 mg/dL).

In addition of the threshold of ≤ 3.9 mmol/L (≤ 70 mg/dL), hypoglycemia episodes with a plasma glucose of <3.0 mmol/L (<54 mg/dL) will be analyzed separately.

Any hypoglycemic event fulfilling the criteria of a SAE or leading to unconsciousness, coma, or seizure will also be recorded as a SAE (see [Section 2.1.4.2](#)).

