## Severe hypoglycemia

Severe hypoglycemia is an event requiring assistance of another person to actively administer carbohydrate, glucagon, intravenous glucose or other resuscitative actions. These episodes may be associated with sufficient neuroglycopenia to induce seizure, unconsciousness or coma.

Self-monitored plasma glucose values may not be available, but neurological recovery attributable to the restoration of plasma glucose to normal is considered sufficient evidence that the event was induced by a low plasma glucose concentration.

**Note:** “requiring assistance of another person” means that the patient could not help himself or herself to treat the hypoglycemia. Assisting a patient out of kindness, when assistance is not required, should not be considered a “requires assistance” incident.

Any hypoglycemic event which leads to unconsciousness, coma, or seizure should also be reported as an SAE.

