Sustained ≥50% decrease in eGFR	
(1) For ≥50% decrease in eGFR from baseline,
 
(1a) confirmed ≥50% decrease in GFR for ≥30 days with no reversible cause as recorded in eCRF "eGFR decrease", OR
 
(1b) positively adjudicated by CEC: Yes to the question "Does the subject meet the criteria of CKD progression" for ≥50% decrease in eGFR.

Sustained eGFR <15 mL/min/1.73 m ²	
(2) For eGFR <15 mL/min/1.73 m²,
 
(2a) confirmed eGFR <15 mL/min/1.73 m² for ≥30 days with no reversible cause as recorded in eCRF "eGFR decrease", OR
 
(2b) positively adjudicated by CEC: Yes to the question "Does the subject meet the criteria of CKD progression".

Chronic dialysis	
(3) For dialysis,
 
(3a) dialysis lasted for ≥90 days (e.g. end date – start date+ 1 ≥90) as recorded in eCRF "Renal Event – Dialysis", OR

Statistical Analysis Plan

Version: 3

Lexicon Pharmaceuticals Protocol No. EFC14833

Date of Issue: 21-Nov-2019

Covance Study ID: 000000150524

AE Grouping	Criteria
	(3b) positively adjudicated by CEC: Yes to the question “. Does the subject meet the criteria for ESRD”.
Renal transplant *	(4) “Renal transplant” captured in eCRF “Other procedure form”, where adjudication is not required. PTs of Renal transplant (10038533), Renal and pancreas transplant (10052278), Renal and liver transplant (10052279) based on MedDRA v22.0.
Renal death	(5) Renal death as positively adjudicated by CEC: “Death - Non-Cardiovascular (Renal)” as the primary cause of death
EOSI not adjudicated *	
Severe hypoglycemia	algorithm specified in Section 2.1.4.1 based on eCRF “Hypoglycemic Events”
Genital mycotic infections	PTs in Appendix C
Urinary tract infections	PTs in Appendix C
Clinically relevant volume depletion and events related/possibly related to volume depletion	PTs in Appendix C
Diarrhea	Narrow search on “Noninfectious diarrhoea (SMQ)” [20000218] plus the following PTs (MedDRA v22.0): Gastroenteritis (10017888), Antidiarrhoeal supportive care (10055660), Enteritis (10014866), Enteritis leukopenic (10014877), Enterocolitis (10014893), Enterocolitis haemorrhagic (10014896)
Pancreatitis	PTs in Appendix C
Venous thrombotic events	PTs in Appendix C

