2.4.5.1 Analyses of hypoglycemia

Analyses of hypoglycemia will be performed on the TEAE period as defined in [Section 2.1.4](#). Hypoglycemia will be classified as severe hypoglycemia, documented symptomatic hypoglycemia, asymptomatic hypoglycemia, probable symptomatic hypoglycemia or relative hypoglycemia (see [Section 2.1.4.1](#)).

The number (%) of patients with any hypoglycemia, severe hypoglycemia and documented symptomatic hypoglycemia will be summarized respectively by treatment group during the TEAE period, as well as the incidence rate in patient years. Two types of incidence rates will be presented: the number of patients with at least 1 event per 100 patient-years (calculated as the number of patients with at least 1 event / total exposure in 100 patient-years), and the number of events per 100 patient-years (calculated as the total number of events / total exposure in 100 patient-years). Note: here exposure (in days) is the duration of TEAE period, ie, duration of IMP treatment in days +1 (see [Section 2.1.4](#)).

Statistical Analysis Plan

Version: 3

Lexicon Pharmaceuticals Protocol No. EFC14833

Date of Issue: 21-Nov-2019

Covance Study ID: 000000150524

The summary of frequency and incidence rate in patient years for severe hypoglycemia or documented symptomatic hypoglycemia will be provided as appropriate by gender (Male, Female), age group (<50, \geq 50 to <65, \geq 65 years), race (White, Black or African American, Asian, Other).

A KM curve will also be provided by treatment group for the time to first severe hypoglycemia or documented symptomatic hypoglycemia during the TEAE period (see [Section 2.5.4](#)).

Documented symptomatic hypoglycemia maybe presented by \leq 3.9 mmol/L (\leq 70 mg/dL) and $<$ 3.0 mmol/L ($<$ 54 mg/dL) respectively, as appropriate.

A listing of patients for all events reported on the dedicated e-CRF “Hypoglycemic event information” page will be provided with each category flagged (ie, severe hypoglycemia, documented symptomatic hypoglycemia, asymptomatic hypoglycemia, probable symptomatic hypoglycemia and relative hypoglycemia).

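### The SAP's severe-hypoglycemia algorithm adds a symptom condition that the definition lacks, so an assisted record with symptoms answered No or left blank falls into none of the five categories (minor)

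*SAP*

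**What the plan says.** The protocol defines the event in Section 10.6.1, under its severe hypoglycemia heading: "Severe hypoglycemia is an event requiring assistance of another person to actively administer carbohydrate, glucagon, intravenous glucose or other resuscitative actions". Neuroglycopenia is mentioned there as something that may accompany the event. The SAP opens Section 2.1.4.1 with the same definition.

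The SAP then turns this into an e-CRF rule with two conditions that must both hold:

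- the option "Subject was Not Capable of Treating Self and Required Assistance" is ticked under the countermeasure question; and
- "To the question “Were Symptoms Present”, ticked “Yes".

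The documented symptomatic, asymptomatic, probable symptomatic and relative categories each carry the opposite first condition: "NOT ticked the option “Subject was Not Capable of Treating Self and Required Assistance".

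Table 3 in SAP Section 2.1.4.2 places severe hypoglycemia among the events of special interest that are not adjudicated. Its only source there is the "algorithm specified in Section 2.1.4.1 based on eCRF “Hypoglycemic Events" page.

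SAP Section 2.4.5.1 states that hypoglycemia will be classified into the five categories, and reports as follows: "The number (%) of patients with any hypoglycemia, severe hypoglycemia and documented symptomatic hypoglycemia will be summarized respectively by treatment group". It also plans incidence rates per 100 patient-years, subgroup tables and a Kaplan-Meier curve for severe or documented symptomatic events, and a listing of every event on the e-CRF page with its category flagged.

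**The concern.** The operational rule is narrower than the definition it implements. The symptom condition can only remove events from the severe category, and the remaining categories cannot take them back because each excludes assisted events. The classification that Section 2.4.5.1 calls for cannot then be carried out for these records.

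Severe hypoglycemia is a named safety endpoint and an event of special interest. Table 3 gives it no adjudication and no preferred-term search as a second route. Few such events may occur, so a single misclassified record could change how an arm looks.

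The direction also differs from the SAP's handling of incomplete safety data elsewhere. In Sections 2.4.5.2 and 2.5.3, an unclear onset date leads to classification as treatment-emergent, and a missing causality assessment is treated as related. Section 2.5.3 has no rule for a blank symptoms answer, so here missing information lowers the count.

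**Working it through.** The plan gives no figure to reproduce on this point; the check is one of logic. The five rules in SAP Section 2.1.4.1 are:

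| Category | Assistance option | Symptoms | Glucose before countermeasure | Further condition |
|---|---|---|---|---|
| Severe | ticked | Yes | any or none | none |
| Documented symptomatic | not ticked | Yes | ≤3.9 mmol/L | none |
| Asymptomatic | not ticked | No | ≤3.9 mmol/L | none |
| Probable symptomatic | not ticked | Yes | not measured | improvement after countermeasure |
| Relative | not ticked | Yes | >3.9 mmol/L | none |

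**Step 1: all possible records.** Assistance has 2 states (ticked, not ticked). Symptoms have 3 (Yes, No, blank). Glucose has 4 (<3.0, 3.0 to 3.9, >3.9 mmol/L, none). Recovery has 2 (Yes; No or blank). This gives 2 × 3 × 4 × 2 = 48 combinations, of which 24 are assisted.

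**Step 2: assisted records under the rules as written.**
- Symptoms Yes: 1 × 4 × 2 = 8 combinations, all severe.
- Symptoms No or blank: 2 × 4 × 2 = 16 combinations, none of them in any category, even with glucose below 3.0 mmol/L.

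**Step 3: assisted records with the assistance tick alone.** All 24 are severe. Unclassified assisted combinations fall from 16 to 0, and no combination lands in two categories.

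**Step 4: non-assisted records.** 13 of 24 are unclassified before and after the change: 8 with symptoms blank, 4 with symptoms No and glucose above 3.9 mmol/L or missing, and 1 with symptoms Yes, no glucose and no recorded recovery. A blank symptoms answer is thus a wider gap than the severe category alone.

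These are counts of logical combinations. They say nothing about how many patients would be affected.

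**Step 5: size of one lost patient.** SAP Section 1.3 gives 76 patients randomized 1:1 and about 300 randomized 1:1:1. The 400 mg and placebo groups are then 76/2 + 300/3 = 138 each, and the 200 mg group is 300/3 = 100. Assuming all are treated, one patient is 1/138 = 0.7 percentage points or 1/100 = 1.0 percentage point.

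**Step 6: where the record goes.**

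| Output | Assisted record, symptoms No or blank |
|---|---|
| Severe count and incidence rates | absent |
| Event of special interest (Table 3) | absent |
| Severe/documented subgroup tables | absent |
| Time to first severe/documented event | absent |
| Any-hypoglycemia count | present |
| Listing of all events | present, no category flag |
| SAE tables (SAP Section 2.4.5.2) | present if treatment-emergent and SAE criteria are met, or if unconsciousness, coma or seizure occurred |

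**The case against.** The best defence is that a correctly completed form cannot produce the gap. Both documents list confusion, seizures, unconsciousness and coma among the symptoms of hypoglycemia. The footnote to Figure 1 in the protocol ties inability to self-treat to acute neurological impairment. The e-CRF asks whether symptoms were present, not whether the patient reported them. A reader might infer that a patient found unresponsive would be missed; the documents do not support that, because unresponsiveness of this kind is itself a listed symptom and should be answered Yes. On this view the second condition merely restates the first. Protocol Section 13.4 also requires complete case report forms and answers to data queries.

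Most of this stands. It confines the problem to records that are inconsistent (assistance ticked, symptoms No) or incomplete (symptoms blank). It does not remove the problem. If the condition is redundant on good records, its only effect is on poor ones, and there it takes the event out of the severe category. General querying does not say how a record that stays unresolved is classified.

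A second objection also has weight: dropping the condition is not free. A wrongly ticked assistance box would count as severe. So would an assisted record with no symptoms and glucose above 70 mg/dL or not measured. The protocol itself cautions against counting help that was not needed.

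**Conclusion.** The mismatch is real and minor. As written, the algorithm does not match the definition in Protocol Section 10.6.1 and the SAP narrative, and any error runs toward undercounting severe events. The number affected cannot be derived from the documents and may be zero. The 0.7 to 1.0 percentage point above is the effect of one assumed patient, not an estimate. SAP Section 2.4.5 makes the safety analyses essentially descriptive, with no systematic testing planned, so no hypothesis test is affected.

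A reader might go further and infer that such events vanish from safety reporting. They do not: the any-hypoglycemia count, the listing and, for the gravest events, the SAE tables still hold them. An assisted event that does not meet SAE criteria has only the first two.

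The conclusion assumes that the e-CRF accepts an assisted record with symptoms No or blank; the form is not in the documents. Only the footnote of Figure 1 could be read in the text available. If the figure has a symptom branch under severe events, the protocol text and figure would themselves need reconciling.

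**What to change.** In SAP Section 2.1.4.1, remove the symptom condition from the severe algorithm, so that the assistance tick alone identifies a severe event, and check the result against Figure 1 of the protocol. Table 3 needs no edit, since it points to that section.

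Add one sentence on data handling: before database lock and unblinding, every assisted record with symptoms No or blank is queried; if it remains unresolved, it is counted as severe and flagged in the listing. The query should also confirm that the assistance box was ticked correctly, particularly where glucose is above 70 mg/dL or missing. This deals with the risk of overcounting, and the flag lets a reader see how far the count depends on such records.

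The cost is a line or two of SAP text, one program condition and possibly a few queries, with no new data collected. Making the change before unblinding avoids any appearance that reclassification followed the results.

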2.1.4.2 Adverse events variables

Adverse event observation period

- Pretreatment adverse events are adverse events that developed or worsened or became serious from the signed informed consent date up to first administration of double-blind IMP.
- Treatment-emergent adverse events are adverse events that developed or worsened or became serious during the treatment-emergent adverse event period.
- Posttreatment adverse events are adverse events that developed or worsened or became serious during the posttreatment period.

All adverse events (including SAE, AESI and EOSI will be coded to a lower-level term (LLT), preferred term (PT), high-level term (HLT), high-level group term (HLGT), and associated primary system organ class (SOC) using the version of MedDRA currently in effect at Covance at the time of database lock.

The occurrence of adverse events (including SAE, AESI and EOSI) will be recorded from the time of signed informed consent until the end of the study (see [Section 2.1.4](#)) or the resolution/stabilization of all SAE, AESI and EOSI.

AESI include:

- Pregnancy

Statistical Analysis Plan

Version: 3

Lexicon Pharmaceuticals Protocol No. EFC14833

Date of Issue: 21-Nov-2019

Covance Study ID: 000000150524

- Symptomatic overdose with IMP/NIMP
- Alanine aminotransferase (ALT) increase > 3 times upper limit of normal (ULN)

EOSI include:

- Major adverse cardiovascular events (MACE [cardiovascular death, myocardial infarction, or stroke]) and other specific cardiovascular (CV) events (eg, heart failure requiring hospitalization)
- Severe hypoglycemia
- Genital mycotic infections (to include vulvovaginal candidiasis in females and candida balanitis in males)
- Urinary tract infection
- Clinically relevant volume depletion and events related/possibly related to volume depletion
- Diarrhea
- Pancreatitis
- Bone fractures
- Venous thrombotic events, to include deep venous thrombosis and thromboembolism (to include pulmonary embolism)
- Diabetic ketoacidosis
- Renal events, to include 50% decline in eGFR, end stage kidney disease, renal death
- Malignancies of special interest (breast, bladder, renal cell, Leydig cell, pancreatic, prostate, and thyroid cancer)
- Adverse event leading to an amputation.

A Clinical Endpoint Committee(s) (CEC) will in a blinded manner review and adjudicate all deaths, myocardial infarction, stroke, unstable angina requiring hospitalization, and heart failure requiring hospitalization, selected renal events, bone fracture, and diabetic ketoacidosis.

Two independent committees will review safety events that require ongoing monitoring to ensure timing protocol amendments in case a safety signal is identified. These events are: 1) potential cases of drug-induced liver injury (DILI), and 2) cases of amputations. The two committees will review the cases in a treatment-blinded manner and will present their assessment to the DMC.

AESI and EOSI will be identified based on criteria in [Table 3](#).

Table 3 - Criteria for AESI and EOSI

Statistical Analysis Plan

Version: 3

Lexicon Pharmaceuticals Protocol No. EFC14833

Date of Issue: 21-Nov-2019

Covance Study ID: 000000150524

AE Grouping	Criteria
AESI	
Pregnancy	eCRF "Pregnancy"
Symptomatic overdose with IMP/NIMP	"Overdose of IMP" or "Overdose of NIMP" checked and "Symptomatic overdose" checked in eCRF "Overdose"
ALT increase > 3X ULN	eCRF "ALT increase"
EOSI adjudicated	
Cardiovascular death	Positively adjudicated by CEC: "Cardiovascular" or "Undetermined" as the primary cause of death
Myocardial infarction, Unstable Angina requiring hospitalization	Positively adjudicated by CEC: Yes to the question "Does the event meet the definition of an MI for this study?", or Yes to the question "If event is not an MI, does the event meet the definition of an UA Requiring admission to hospital or emergency room, for this study?"
Stroke	Positively adjudicated by CEC: Yes to the question "Does the event meet the definition of a Stroke for this study?"
Heart failure requiring hospitalization	Positively adjudicated by CEC: Yes to the question "Does the event meet the definition of a Heart Failure Event for this study?"
Bone fractures	Positively adjudicated by CEC: Yes to the question "Did the Fracture occur?"
Diabetic ketoacidosis	Positively adjudicated by CEC: Yes to the question "Does this event meet the criteria to be a DKA event?"
EOSI Renal events where select events adjudicated	
Sustained ≥50% decrease in eGFR	
(1) For ≥50% decrease in eGFR from baseline,
 
(1a) confirmed ≥50% decrease in GFR for ≥30 days with no reversible cause as recorded in eCRF "eGFR decrease", OR
 
(1b) positively adjudicated by CEC: Yes to the question "Does the subject meet the criteria of CKD progression" for ≥50% decrease in eGFR.

Sustained eGFR <15 mL/min/1.73 m ²	
(2) For eGFR <15 mL/min/1.73 m²,
 
(2a) confirmed eGFR <15 mL/min/1.73 m² for ≥30 days with no reversible cause as recorded in eCRF "eGFR decrease", OR
 
(2b) positively adjudicated by CEC: Yes to the question "Does the subject meet the criteria of CKD progression".

Chronic dialysis	
(3) For dialysis,
 
(3a) dialysis lasted for ≥90 days (e.g. end date – start date+ 1 ≥90) as recorded in eCRF "Renal Event – Dialysis", OR

Statistical Analysis Plan

Version: 3

Lexicon Pharmaceuticals Protocol No. EFC14833

Date of Issue: 21-Nov-2019

Covance Study ID: 000000150524

AE Grouping	Criteria
	(3b) positively adjudicated by CEC: Yes to the question “. Does the subject meet the criteria for ESRD”.
Renal transplant *	(4) “Renal transplant” captured in eCRF “Other procedure form”, where adjudication is not required. PTs of Renal transplant (10038533), Renal and pancreas transplant (10052278), Renal and liver transplant (10052279) based on MedDRA v22.0.
Renal death	(5) Renal death as positively adjudicated by CEC: “Death - Non-Cardiovascular (Renal)” as the primary cause of death
EOSI not adjudicated *	
Severe hypoglycemia	algorithm specified in Section 2.1.4.1 based on eCRF “Hypoglycemic Events”
Genital mycotic infections	PTs in Appendix C
Urinary tract infections	PTs in Appendix C
Clinically relevant volume depletion and events related/possibly related to volume depletion	PTs in Appendix C
Diarrhea	Narrow search on “Noninfectious diarrhoea (SMQ)” [20000218] plus the following PTs (MedDRA v22.0): Gastroenteritis (10017888), Antidiarrhoeal supportive care (10055660), Enteritis (10014866), Enteritis leukopenic (10014877), Enterocolitis (10014893), Enterocolitis haemorrhagic (10014896)
Pancreatitis	PTs in Appendix C
Venous thrombotic events	PTs in Appendix C
Malignancies of special interest	Breast cancer: Narrow search on “Breast neoplasms, malignant and unspecified (SMQ)” [20000149] Prostate cancer: Narrow search on “Prostate neoplasms, malignant and unspecified (SMQ)” [20000152] Leydig-cell cancer: PTs of Leydig cell tumour of the testis (10024407) and Ovarian Sertoli-Leydig cell tumour (10073270) based on MedDRA v22.0 Thyroid cancer: PTs in Appendix C Renal cell cancer: PTs in Appendix C Pancreatic cancer: PTs in Appendix C Bladder cancer: PTs in Appendix C

EOSI AE leading to an amputation

Statistical Analysis Plan

Version: 3

Lexicon Pharmaceuticals Protocol No. EFC14833

Date of Issue: 21-Nov-2019

Covance Study ID: 000000150524

AE Grouping	Criteria
Adverse event leading to an amputation	"AE Correction" as the reason for amputation in eCRF "Other Procedures related to Amputation"
AE potentially leading to an amputation *	PTs in Appendix C

* Search terms will be updated using the MedDRA version currently in effect at Covance at the time of database lock for EOSI identified by them.

AE potentially leading to an amputation: not an EOSI per individual protocol; analyzed due to their relevance to lower limb complication and amputations as a requirement from health authorities.

